#### 9.3.4. Exit Procedures

In the event of premature exit from the study, all study-related examinations should be completed whenever possible. The Exit CRF should be completed, noting that the subject did not complete the study and the reason for premature study exit. If no premature exit from the study occurs, the Exit CRF should be completed at the end of Visit 5 (3 Months Postoperative).

### **9.4. Study Methods and Measurements**

All routine testing and basic eye examinations (the usual standard of care for the practice) should be carried out at each study visit. Abnormalities should be recorded in the CRF “Comment” section. Specific study examination procedures are outlined below.

#### 9.4.1. Manifest refraction

Perform a manifest refraction with a high contrast logMAR ETDRS chart under photopic lighting conditions ( $>85$  cd/m^2). Document refraction results with sphere, cylinder and axis readings using the ETDRS protocol. If uncorrected visual acuity is not improved by manifest refraction, use zero for sphere and cylinder and draw a line through the blank for the axis. All visual acuities should be recorded as letters read on the ETDRS chart.

#### 9.4.2. Visual acuity (VA)

Measure uncorrected and corrected distance visual acuity using the MR according to the ETDRS protocol using 100% contrast letters. Record visual acuities as number of letters read on the ETDRS chart.

#### 9.4.3. Corneal aberrations

Measure the corneal topographic aberrations with the Pentacam analyzer.

#### 9.4.4 Ocular high order aberrations

Measure ocular HOA at sites appropriately equipped to do so. The device used to measure HOA's should be indicated, and a 5 mm pupil size should be selected where feasible.

#### 9.4.5. Subjective questionnaire

Have the subject complete the subjective questionnaire.

Note: Avoid interpreting survey questions for subjects. That is, avoid re-phrasing questions if subjects ask, “What does this mean?”

### **9.5. *Unscheduled Visits***

Unscheduled exams may be conducted at the discretion of the investigator with all relevant information from the exam recorded in the source documents and on the Unscheduled Visit pages within the CRF booklet.

### **9.6. *Discontinued Subjects***

Discontinued subjects are those who do not have an exit visit or who come into the office to be exited prior to the scheduled final study visit. Subjects may be discontinued from the study at any time if, in the opinion of the investigator, their continued participation in the study poses a risk to their health. The reasons for discontinuation include:

- a. Adverse event;
- b. Lost to follow-up;
- c. Subject decision unrelated to an adverse event;
- d. Protocol violation;
- e. Treatment failure;
- f. Fear of exposure to infectious disease
- g. Other.

To ensure the safety of all subjects who discontinue prior to Visit 5, investigators should assess each subject and, if necessary, advise them of any therapies and/or medical procedures that might be needed to maintain their health. Any changes in medical health and/or use of concomitant medications should also be captured.

## **10. ANALYSIS PLAN**

### **10.1. *Analysis Data Sets***

All subjects who are enrolled in the study will be evaluated for safety. Efficacy analyses will be performed based on data from those eyes for which uncomplicated LASIK was completed.

### **10.2. *Statistical Methodology***

All data will be collected by the site and entered into a spreadsheet. Subjects will be assigned an ID number. Data analysis will be performed without patient identification. Statistical analysis will be performed using standard descriptive statistics and other tests as deemed appropriate based on the characteristics of the data to be analyzed. All statistical tests will be two-sided and interpreted at a 5% significance level.

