### 3. GENERAL INFORMATION

Objective	
The objective of the current study is to prospectively evaluate 3-month clinical outcomes from LASIK performed using the Phorcides surgical planning software with Contoura topography-guided ablation in both eyes of subjects with myopia and myopic astigmatism seeking refractive surgery for distance correction. Data will be compared to published results for wavefront optimized LASIK and LASIK performed with Contoura using other refractive algorithms.
 
The hypothesis is that use of the Phorcides planning software will result in a higher percentage of eyes with residual refractive cylinder <math>\leq 0.25D</math> than will be achieved with wavefront-optimized (WFO) LASIK. It is also expected that unaided postoperative visual acuity and visual symptoms will be improved.

Test Article(s)	Phorcides Analytical Engine refractive surgery planning software
Control Article(s)	None
Sample size	140 eyes of 70 subjects
Study Population	Subjects $\geq 20$ years of age with myopia and myopic astigmatism, who are suitable candidates for LASIK, meet the approved range of treatment for Contoura topography-guided LASIK and desire optimal uncorrected distance visual acuity in both eyes.
Number of sites	Four
Study Design	Prospective, single arm, open-label study.
Masking	None
Variables	Primary: 

● Residual refractive cylinder

 Secondary: 

● Monocular uncorrected distance visual acuity

- Monocular corrected distance visual acuity
- Residual refractive sphere
- Corneal aberrations
- Ocular aberrations (at sites equipped for such measurement)
- Subjective questionnaire evaluating visual symptoms such as light sensitivity glare, halos, and starbursts

Duration / Follow-up    Preoperative to 3 months postoperative

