## 5. INTRODUCTION

The Contoura software for the Alcon WaveLight excimer laser was approved several years ago, but some surgeons are unsure about how to plan treatments when the manifest cylinder determined by refraction differs significantly from the Contoura-derived cylinder. This has caused some surgeons to abandon the Contoura procedure. The Phorcides Analytical Engine (Phorcides) refractive surgical planning software has demonstrated efficacy in addressing this issue. Use of the Phorcides software is expected to simplify surgical planning and improve overall outcomes with topography-guided ablations; as a result, it may increase use of Contoura in clinical practice.

It is expected that clinical refractive outcomes with Phorcides will be superior to those obtained with wavefront-optimized refractive surgery using the same laser that have been reported in the literature. It is also expected that results with Phorcides will be superior to, and more consistent than, Contoura results reported in the literature that were based on alternative algorithms.

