## 6. OBJECTIVE

The objective of the study is to prospectively compare 3-month clinical outcomes of LASIK performed using the Phorcides surgical planning software with Contoura topography-guided ablation to wavefront-optimized (WFO) LASIK results and Contoura results based on other algorithms reported in the literature.

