### 7.2. Inclusion Criteria

Subjects are eligible for the study if they meet the following criteria:

**Note:** Ocular criteria must be met in both eyes.

- Candidate for Contoura excimer laser vision correction
- Gender: males and females.

- Age: 20 or older
- Willing and able to provide written informed consent for participation in the study.
- Willing and able to comply with scheduled visits and other study procedures.
- Good ocular health, with no pathology that compromises visual acuity (other than refractive error)
- Corrected preoperative visual acuity of 20/20 (0.0 logMAR) or better in the eye being treated
- Meet Contoura eligibility requirements (approved range): up to -8.00 D sphere, up to -3.00 D cylinder, and a spherical equivalent no greater than -9.00 D
- Desire good vision at distance in both eyes

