### **7.4. Exclusion Criteria during surgery**

The following exclusion criteria are applicable to the study eye during the study

- Intraoperative complications.

Any subject whose surgery has been aborted for either eye should immediately be discontinued from the study and an exit form completed for that subject. These subjects will be followed according to the clinic standard of care and monitored for safety, but their data will be excluded from the study efficacy analysis. All adverse events will be appropriately documented and reported.

Participants who are considered to be in a vulnerable population will not be enrolled into the study. Vulnerable populations include, but are not limited to, the following:

- Prisoners
- Nursing home residents
- Institutionalized individuals
- Mentally disabled and cognitively impaired individuals
- Sponsor employees and their family members
- Site employees and their family members that are directly or indirectly involved in the study
- Economically disadvantaged individuals
- Educationally disadvantaged individuals
- Adults who do are illiterate
- Subjects who are deaf or have a severe hearing disability
- Terminally ill individuals
- Individuals with life-threatening conditions

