### ***8.2. Methods Used to Minimize Bias***

This is a single-arm study with both eyes of any subject enrolled. Patients will not be pre-selected for study inclusion. Any eligible patient presenting for, and eligible for, binocular Contoura treatment may be invited to participate.

The measurement of the postoperative refraction and visual acuity will be conducted in a systematic fashion to minimize bias. Individuals conducting visual acuity measures will be refracted with the methodology used in the Early Treatment Diabetic Retinopathy Study, with the same level of encouragement to subjects. Subjective questions will be asked in a similar manner to all patients. Alternatively, at the discretion of the investigator, patients may be asked to complete the questionnaire themselves.

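### The share of eyes with residual cylinder of 0.25 D or less is to be set against published rates, yet Sections 10.2 and 10.3 plan no use of the preoperative cylinder recorded at Visit 1

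*Combined protocol and SAP*

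**What the plan says.** Section 3 states the claim to be tested: "The hypothesis is that use of the Phorcides planning software will result in a higher percentage of eyes with residual refractive cylinder" of 0.25 D or less than WFO LASIK achieves. It lists no control article and gives the source of the comparison: "Data will be compared to published results for wavefront optimized LASIK and LASIK performed with Contoura using other refractive algorithms". Section 6 names the same external comparators, "wavefront-optimized (WFO) LASIK results and Contoura results based on other algorithms reported in the literature". Section 5 expects that "clinical refractive outcomes with Phorcides will be superior to those obtained with wavefront-optimized refractive surgery using the same laser".

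On who enters, Section 7.2 bounds cylinder on one side only: "Meet Contoura eligibility requirements (approved range): up to -8.00 D sphere, up to -3.00 D cylinder". Section 8.2 adds: "Patients will not be pre-selected for study inclusion".

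On who is analysed, Section 10.1 limits efficacy to eyes whose LASIK was finished without complication. For subjects with surgery aborted in either eye, Section 7.4 says "their data will be excluded from the study efficacy analysis". Neither rule concerns cylinder.

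On what is measured, Tables 9.3-2 and 15.1 schedule a manifest refraction at Visit 1, and Section 9.4.1 has its cylinder written down.

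On analysis, Section 10.2 offers: "Statistical analysis will be performed using standard descriptive statistics and other tests as deemed appropriate based on the characteristics of the data". It adds two-sided testing at 5%, and Section 10.3 adds the software and repeats the significance level. Sections 10.1, 11 and 13.5 do not mention preoperative cylinder either.

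**The concern.** Preoperative cylinder is the starting value of the primary variable. With no lower limit, an eye can enter already at 0.25 D or less and count as a success with little or no astigmatic correction. An eye near the -3.00 D limit has much further to go. The pooled percentage may therefore depend on the mix of eyes as well as on how well surgery was planned.

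Randomisation would balance that mix; a comparison with a published series does not. Recruiting without pre-selection limits selection inside this study but cannot make its mix match another series.

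At stake is the reading of the main result. A favourable percentage could partly reflect easier eyes, and an unfavourable one harder eyes. Because Section 10.2 lets the choice of tests follow the data, whether to adjust, and to which series, could be settled after results are seen.

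This point concerns case mix only. Naming a reference rate and a test would not resolve it.

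**Working it through.** **The plan's own figure.** Section 11 expects 10% dropout from 140 eyes: 140 × (1 − 0.10) = 126, as stated. The plan gives no reference rate, effect size or power, so nothing else can be reproduced. Every share, success rate and correlation below is an assumption for illustration.

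**1. Shift from mix alone, two groups.** Let the share of low-cylinder eyes differ by 20 points between study and comparator, with success s in low-cylinder eyes and o in the rest, the same in both series. Shift = 0.20 × (s − o).
- s = 0.85, o = 0.80: 1.0 point
- s = 0.95, o = 0.70: 5.0 points
- s = 1.00, o = 0.60: 8.0 points
- s = o: 0 points

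**2. Sampling error for comparison.** Half-width = 1.96 × √[p(1 − p)(1 + ρ)/n], with two eyes per subject and between-eye correlation ρ. For n = 126:
- ρ = 0: 7.0 points at p = 0.80; 8.0 at p = 0.70
- ρ = 0.5: 8.6 and 9.8 points

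Most of the shifts in step 1 are smaller than this. Unlike sampling error, though, they do not shrink as eyes are added.

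**3. Three groups, either direction.** Take success rates of 95/80/60% for low, middle and high cylinder, identical in both series.
- Mix 30/40/30%: 0.30 × 95 + 0.40 × 80 + 0.30 × 60 = 78.5%
- Mix 10/40/50%: 0.10 × 95 + 0.40 × 80 + 0.50 × 60 = 71.5%

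If the study has the first mix and the comparator the second, the study looks 7.0 points better with no true difference. With the mixes exchanged it looks 7.0 points worse. Standardising to the comparator's mix brings the difference to zero in both cases.

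**4. Effect on a test.** Take rates of 95/85/65%, again identical in both series. A study mix of 50/35/15% gives 87.0%. Published mixes of 35/35/30% and 20/40/40% give 82.5% and 79.0%. The spurious gain is 4.5 to 8.0 points. With an exact binomial test against the published rate taken as fixed (nominal upper tail 2.5%), the chance of a false finding of superiority is:
- 126 independent eyes: 23% to 63%
- information equivalent to only 63 subjects: 7% to 27%
- flatter gradient of 90/85/75% (gain 2.25 to 4.0 points): 9% to 21% with 126 eyes, 5% to 11% with 63

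**5. Precision after standardising.** Half-width = 1.96 × √[(1 + ρ) × Σ w²r(1 − r)/n_k], where w is the comparator's share, r the success rate and n_k the study eyes in category k. Rates are those of step 3.
- Study 30/40/30%, comparator 10/40/50%: 7.2 points crude, 9.0 standardised (8.8 and 11.0 with ρ = 0.5)
- Mixes exchanged: 7.9 crude, 6.8 standardised
- A single stratum of 42 eyes at p = 0.80 to 0.70: 12.1 to 13.9 points (14.8 to 17.0 with ρ = 0.5)
- Sparse cells: if a category with 50% of the comparator weight holds 2 study eyes (62/62/2), 34.2 points; with 10 eyes (58/58/10), 15.7
- Merging: with 62/55/9 eyes and the 10/40/50% comparator, full standardisation gives 71.5% with a half-width of 16.6. Merging the last two categories gives 79.0% with a half-width of 9.3, so 79.0 − 71.5 = 7.5 points of mix stay unadjusted.

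**The case against.** Four objections deserve an answer.

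*No passage says the comparison will be crude.* True. Section 10.2 is silent and would permit adjustment, and Sections 3 and 8 list the primary variable as residual cylinder without the 0.25 D cut-off, which appears only in the hypothesis. But permission is not prespecification, and the open wording is what leaves the choice until after the data are seen.

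*No consequence follows from the documents themselves.* This stands. Whether any comparator's mix differs, or is even published by category, cannot be known from them. The 23% to 63% range uses assumed mixes 15 to 30 points apart and independent eyes, and it falls sharply when either assumption is relaxed. It shows what is possible and should not be quoted as the trial's error rate.

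*The root gap is that no series, rate or test is named.* Partly right: standardising needs a listed comparator. Yet a named rate and test would leave the mix problem where it is, and reporting by preoperative cylinder needs no comparator data.

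*Adjustment costs precision and may rarely be feasible.* Also right, which is why it belongs beside the all-eyes result and should not replace it.

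A reader might go further and infer that the comparison is biased in favour of the Phorcides software, that low-cylinder eyes should not be enrolled, or that superiority may not be claimed without adjustment. The documents support none of these. The direction is unknown, the eligibility range is stated to be the approved one, and a ban would be hard to apply consistently: in the merging example an adjusted comparison still carries 7.5 points of mix.

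**Conclusion.** The gap is real and limited. The hypothesis rests on an external comparison of a percentage that may depend on preoperative cylinder. Eligibility admits low-cylinder eyes without a floor, the needed measurement is taken at Visit 1, and no section plans to use it. A difference in mix could create or conceal an apparent advantage.

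Under the assumed inputs the size is about 0 to 8 points, against a 95% half-width of about 7 to 10 points for 126 eyes, so it need not change the conclusion. It vanishes if success does not vary with preoperative cylinder or if the mixes match. The omission can be read directly from the text; its size cannot. No stated number is wrong, and the study is not shown to be invalid. This is a cheap improvement.

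**What to change.** Keep eligibility, the efficacy set of Sections 7.4 and 10.1, and the all-eyes percentage as the primary result. Add to Section 10.2:

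(a) *The percentage of eyes with residual refractive cylinder of 0.25 D or less at 3 months will also be reported by preoperative manifest cylinder (0.25 D or less; above 0.25 to 1.00 D; above 1.00 D; or the comparator's categories where published), merging sparse categories and naming any merged, with 95% intervals that account for two eyes per subject.*

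(b) *The published comparator series will be listed before any postoperative refraction data are reviewed. For each that reports preoperative cylinder by category, the study percentage standardised to that distribution will be shown as a sensitivity analysis beside the crude comparison, and a superiority statement will note whether both agree. Where no distribution is published, the comparison will be described as unadjusted for case mix.*

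(c) *The report will state that standardising on cylinder does not remove differences in sphere, age or surgical technique.*

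The timing in (b) matters because the study is open-label and refraction is repeated at 1 month, so listing series only before the 3-month analysis would be too late. The cut-points in (a) are a proposal, not taken from the documents. The count below which a category is sparse should be written in with the rule.

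Cost: one table and some wording, with no new data. Intervals usually widen (7.2 to 9.0 points in the example), and strata are imprecise (about 12 to 17 points for 42 eyes). If no comparator publishes cylinder by category, the by-cylinder table and the unadjusted label are all that apply.

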### **10.3. *General Statistical Considerations***

The statistical analyses will be performed using Statistica, version 12 or higher. Any statistical tests of hypotheses will employ a level of significance of  $\alpha=0.05$ .

## **11. SAMPLE SIZE JUSTIFICATION**

The sample size has been chosen to be similar to that for comparable Contoura, WFO, WFG and ray tracing LASIK studies published in the peer-reviewed literature. Each of four sites will enroll up to 50 eyes, for a total potential study population of 140 eyes. With an expected 10% dropout rate before the 3M visit, 126 eyes would be available for analysis.

## **12. CONFIDENTIALITY/PUBLICATION OF THE STUDY**

The existence of this study is confidential and should not be discussed with persons who are not involved with the study. Results will be submitted for publication and presentation at national and/or international meetings. A manuscript will be submitted to peer-review journals for publication but there is no guarantee of acceptance. Presentation or publication of data from individual sites or a subset of sites involved in the study is prohibited. The company funding this study may review manuscript(s) prior to publication, but it may not control their content or the interpretation of the results of the study.

All study data will be collected on appropriate Case Report Forms (CRFs). No protected health information will be included on the forms. CRFs will be retained in the patient's file for a minimum period of 3 years. Collected information will be used for purposes of this study and possible future research, but no information will be sold to third parties. The following people will have access to study records:

- Investigators and staff involved with the study
- Study monitor or auditor
- Sponsoring company
- Research institution at which the study is being performed
- Review boards and accrediting agencies
- Other State or Federal regulatory agencies, as permitted by law

The de-identified data may be shared with other researchers for further analysis.

## **13. QUALITY COMPLAINTS AND ADVERSE EVENTS**

All subjects will be monitored for adverse events over the course of the study. A place to record any adverse event is included on each case report form.

### ***13.1. General Information***

An Adverse Event (AE) is any untoward medical occurrence in a subject who is administered a study treatment regardless of whether the event seems to have a causal relationship with the treatment. An AE, therefore, can be any unfavorable or unintended sign (including an abnormal laboratory finding), symptom, or disease temporally associated with the study treatment, whether or not it is related to the treatment. In clinical studies, an AE can include an untoward medical occurrence occurring at any time after the informed consent document is signed, including run-in or washout periods, even if no study treatment has been administered.

### ***13.2. Monitoring for Adverse Events***

At each visit, after the subject has had the opportunity to spontaneously mention any problems, the Investigator should inquire about AEs by asking if the patient has any problems.

### ***13.3. Procedures for Recording and Reporting AEs and SAEs***

Subsequent to signing an informed consent form, all untoward medical occurrences that occur during the course of the study must be documented on an Adverse Event Form (AEF). A separate AEF must be filled out for each event. When possible, signs and symptoms indicating a common underlying pathology should be documented as one comprehensive event. For each recorded event, the AE documentation must include the onset date, outcome, resolution date (if event is resolved), intensity (i.e., severity), any action with study treatment taken as a result of the event, and an assessment of the adverse event's relationship to the study treatment.

